4.5 Treatment Adherence

We will calculate treatment compliance for Phase 1 interventions (MDSF, LAF, RUSF) based on three metrics.

- % of days trial regimen consumed: The % of days that the trial regimen (any amount) was consumed based on regimen logs and participant reports. The denominator will be 84 for those that complete follow or total follow-up days for those with withdrawal, death, censoring. Based on this metric, participants will not be able to exceed 100% adherence if they consume more of the intervention than intended.
- % of daily supplements consumed over follow-up: This will be the average % of the supplement consumed each day of follow-up (e.g. 80% Day 1, 100% Day 2, 0% Day 3 etc.). The number of averaged will be 84 for those that complete follow or total follow-up days for those with withdrawal, death, censoring.
- % of daily supplements consumed among days the child received any supplement: This will be the average % of the supplements consumed on days they receive the regimen, (e.g. 80% Day 1, 100% Day 2, etc.).

4.6 Timing of Analyses and DSMB Stopping Guidance

Interim analyses for the primary outcomes and severe adverse events will be presented to the DSMB by the study arm (but coded to not reveal specific intervention – i.e., red, blue, green groups) per the DSMB charter. For the primary outcomes, the Haybittle-Peto boundary (p<0.001) will be used by the DSMB to guide stopping recommendations. Stopping the trial will also be determined by the DSMB but also considered by the DSMB based on severe adverse event rates, recruitment, and follow-up rates, new external information, or other considerations.

The final analysis will be conducted after all participants have been discharged from the study.

4.7 Pilot Data

Each study site will conduct a pilot of 12 participants before starting the trial. The participants in the pilot will not be analyzed in the trial analysis.

5 Statistical Analysis

5.1 Screening Data

We will report the trial start and end dates for screening as well as the overall number of children screened, the number of screened children and not recruited the reason for non-recruitment, and the number of children enrolled in the trial in a standard trial flow chart. We will also produce a table of these data by study site, which may be considered for a supplemental table in the main trial report.

5.2 Statistical Methods for Primary Outcomes

i. MDSF vs RUSF on 12-week anthropometric recovery (superiority): We will use data from all follow-ups visits up to 12-week visit to define a 12-week anthropometric recovery for each participant. Participants who miss study visits, die, or withdraw from the study will have data from all completed study visits analyzed. If a participant does not complete any follow-up visits at or before the 12-week visit (no follow-up data), they will be excluded from the analysis (complete case). All individuals who have at least 1 follow-up visit will contribute to the analysis. We will not impute missing values for missed visits; the definition of recovery will be based on data available from visits at or before 12 weeks.

We will report the proportion of participants who reached 12-week anthropometric recovery by intervention arm. We will use a log-binomial regression model to present the relative risk (RR) of 12-week anthropometric recovery for the MDSF arm as compared to the RUSF arm. Due to stratified randomization by study site, we will include a fixed effect for the study site in the model. We will present the relative risk, two-sided 97.5% confidence intervals, and a p-value <0.025 will be considered statistically significant (to account for multiple comparisons).

ii. LAF vs RUSF on 12-week anthropometric recovery (non-inferiority): This comparison assesses first-stage randomization options. We will use data from all completed follow-up visits before and at the 12-week visit to define a 12-week anthropometric recovery for each participant. Participants who miss study visits, die, or withdraw from the study will have data from all completed study visits analyzed. If a participant does not complete any follow-up visits at or before the 12-week visit (no follow-up data), they will be excluded from the analysis (complete case). We will not impute missing values for missed visits; the definition of recovery will be based on data available from visits at or before 12 weeks.

We will report the proportion of participants who reached 12-week anthropometric recovery by LAF and RUSF arms. We will use generalized linear models with a binomial distribution and identity link function to produce risk difference estimates for the LAF arm compared to the RUSF arm. Due to stratified randomization by study site, we will include a fixed effect for the study site in the model. The lower bound of the one-sided 97.5% confidence interval (to account for multiple comparisons) of the risk difference arm will be compared with the prespecified noninferiority margin of -5% to assess non-inferiority. We will also present a p-value for non-inferiority, with a p-value <0.025 considered statistically significant. Two-sided 95% confidence intervals will be presented, which have an upper boundary equivalent to a one-sided 97.5% confidence interval.

iii. MDSF vs RUSF on 24-week sustained anthropometric recovery (superiority): This analysis will utilize data from visits during the first 12 weeks in addition to the 24-week visit. Sustained anthropometric recovery is defined by 12-week anthropometric recovery and continued recovery at the 24-week visit.

If a participant does not complete any follow-up visits at or before the 12-week visit (no 12-week follow-up data), they will be excluded from the analysis (complete case). Individuals who reached anthropometric recovery at 12 weeks but do not have anthropometric data at 24 weeks (loss to follow-up/missing data, death, withdrawal) will also be excluded from the analysis (complete case). Individuals who did not reach anthropometric recovery by 12 weeks will be analyzed as not having met 24-week sustained recovery, regardless of completion of the 24-week visit, as by definition, they will not have met sustained recovery.

We will report the proportion of participants who reached sustained anthropometric recovery at 24 weeks by intervention arm. We will use a log-binomial regression model to present the relative risk (RR) of 24-week sustained anthropometric recovery for the MDSF arm compared to the RUSF arm. Due to stratified randomization by study site, we will include a fixed effect for the study site in the model. We will present the relative risk, 97.5% confidence intervals, and a p-value <0.025 will be considered statistically significant (to account for multiple comparisons).

iv. LAF vs RUSF on 24-week sustained anthropometric recovery (superiority): This analysis will utilize data from visits during the first 12 weeks in addition to the 24-week visit. Sustained anthropometric recovery is defined by 12-week anthropometric recovery and continued recovery at the 24-week visit.

If a participant does not complete any follow-up visits at or before the 12-week visit (no 12-week follow-up data), they will be excluded from the analysis (complete case). Participants who reached anthropometric recovery at 12 weeks but do not have anthropometric data at 24 weeks (loss to follow-up/missing data, death, withdrawal) will also be excluded from the analysis (complete case). Participants who did not meet 12-week anthropometric recovery will be analyzed as not having met 24-week sustained

recovery, regardless of their completion of the 24-week visit, as by definition they are known to not have met the sustained recovery endpoint.

We will report the proportion of participants who reached sustained anthropometric recovery at 24 weeks by intervention arm. We will use a log-binomial regression model to present the relative risk (RR) of 24-week sustained anthropometric recovery for the LAF arm compared to the RUSF arm. Due to stratified randomization by study site, we will include a fixed effect for the study site in the model. We will present the relative risk, 97.5% confidence intervals, and a p-value <0.025 will be considered statistically significant (to account for multiple comparisons)

v. Sustained recovery intervention vs standard of care on 24-week sustained anthropometric recovery (superiority):

Given that the second randomization occurs after meeting the 12-week anthropometric outcome, the analysis for 24-week sustained recovery for sustained recovery intervention vs standard of care will only utilize data from the 24-week visit to define the outcome for this comparison.

We will report the proportion of participants who reached sustained anthropometric recovery at 24 weeks by intervention arm. We will use a log-binomial regression model to present the relative risk (RR) of 24-week sustained anthropometric recovery for the sustained recovery intervention as compared to the standard of care arms. Due to stratified randomization by study site, we will include a fixed effect for the study site in the model. We will present the relative risk, 95% confidence intervals, and a p-value <0.05 will be considered statistically significant.

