- 6) Mean change in skinfold thickness measurements from randomization to 24 weeks: This will be the 24-week skinfold thickness measurements minus the randomization measurement value.
- 7) Severe acute malnutrition (SAM) from randomization to 24 weeks. SAM will be defined as a WLZ < -3 z-score or MUAC <115 mm or the presence of bilateral pitting oedema.
- 8) All-cause mortality from randomization to 24 weeks (randomization) to 24 weeks. Deaths that occur on or before day 168 of follow-up will be counted for the 24-week outcome.
- 9) SAM or All-cause mortality from randomization to 24 weeks. This is a composite outcome of SAM or death; if SAM occurs first the date of SAM measurement will be used to define the time period. SAM will be defined as a WLZ < -3 z-score or MUAC <115 mm or the presence of bilateral pitting oedema at any follow-up visit. Deaths that occur on or before day 168 of follow-up will be counted for the 24-week outcome.
- 10) Any hospitalization to 24 weeks: Hospitalization from any cause will be defined as a stay in a health facility >24 hours.

3.3 Trial Sample Size

The trial sample size was based on sample size calculations for the primary outcome analyses. The sample size required for the analysis of non-inferiority of LAF as compared to RUSF on 12-week anthropometric recovery was the largest and therefore determined the overall trial sample size.

Primary Comparison #1- LAF vs RUSF on 12-week anthropometric recovery (non-inferiority): There is some evidence that justifies a non-inferiority comparison between LAF and RUSF. A meta-analysis on the management of acute malnutrition in LMICs suggests no difference in recovery from moderate wasting when standard RUSF was compared to local or homemade food, although this is considered low-quality evidence from only two studies.

The choice of non-inferiority margin was based on the judgment of clinical and public health importance of differences in the primary outcome (in our case, anthropometric recovery by 12 weeks of treatment). The investigator group and WHO staff determined that if the recovery rate with one treatment option was 60% and a non-inferiority margin of a risk difference of -5% is appropriate.

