Based on assumptions of 1:1 randomization, 90% power, a one-sided α =0.025 (0.05/2 for multiple comparisons), 5% loss to follow-up/missing data, and that 60% of participants would have 12-week anthropometric recovery outcome in the RUSF and LAF arms, we would require 2,120 participants in each intervention group. As the rate-limiting randomization #1 sample size, the trial 2,120 participants are enrolled in each of the three first-stage randomization interventions, totaling 6,360 total participants in the trial.

Primary Comparison #2: MDSF vs RUSF on 12-week anthropometric recovery (**superiority**): This hypothesis is based on the evidence from a proof-of-principle study conducted in Bangladesh, which showed that MDSF is better than RUSF in promoting growth. We anticipate that 60% of enrolled children will achieve anthropometric recovery within 12 weeks of enrolment in the RUSF group (comparison group). Based on an enrollment of 2,120 per intervention arm, 1:1 randomization, an α of 0.025 (0.05/2 due to multiple comparisons), and 5% loss to follow-up/missing data, we will have 90% power to detect a relative risk of 1.09 for 12-week anthropometric recovery for MSDF as compared to RUSF.

Primary Comparison #3 MDSF vs RUSF on 24-week sustained anthropometric recovery (superiority): This hypothesis is also based on the evidence from a proof-of-principle study conducted in Bangladesh, which showed that MDSF is better than RUSF in promoting growth.

We anticipate that 40% of enrolled children in the second randomization, therefore 24% overall will achieve 24-week sustained anthropometric recovery in the RUSF group (comparison group). Based on an enrollment of 2,120 per arm, 1:1 randomization, an α of 0.025 (0.05 / 2 due to multiple comparisons), and 10% loss to follow-up/missing data, we will have 90% power to detect a relative risk of 1.21 for 24-week sustained anthropometric recovery for MSDF as compared to RUSF.

Primary Comparison #4 LAF vs RUSF on 24-week sustained anthropometric recovery (**superiority**): We believe that the LAF group could have more sustained recovery than RUSF because it has higher acceptability, lower likelihood of displacing usual diet and breastfeeding, and an easier transition to giving adequate home foods to the child in phase 2 after recovery has been achieved.

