4.3 Missing Data

We will assume that all outcome data will be missing completely at random, and we will use a complete case analysis (only including those with data for the outcome of interest) as the primary analytic strategy. We will not impute values for any missing outcome data. We will compare the characteristics of people loss to follow-up and those with primary outcome data, we will conduct

a sensitivity analysis using inverse probability weighting (IPW) if there is indication of differential missingness/loss to follow-up by treatment arm (p<0.05).

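### Section 5.2 counts children lost before week 12 and not yet recovered as not recovered, which contradicts the complete-case, no-imputation rule of Section 4.3 and can bias the LAF non-inferiority contrast when loss differs by arm

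*SAP*

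**What the plan says.** SAP Section 3.2 defines 12-week recovery as recovery at any visit up to week 12. Section 3.1 has children measured weekly in Phase 1.

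Section 5.2 i (MDSF vs RUSF) excludes a child only if there was no follow-up visit at all, and adds: "All individuals who have at least 1 follow-up visit will contribute to the analysis". Section 5.2 ii (LAF vs RUSF non-inferiority) omits that sentence but has the same exclusion. Both state that "the definition of recovery will be based on data available from visits at or before 12 weeks", and both apply this to children who miss visits, withdraw or die.

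Section 4.3 assumes outcomes are missing completely at random, makes complete-case analysis the primary strategy and states: "We will not impute values for any missing outcome data". Its only back-up is "a sensitivity analysis using inverse probability weighting (IPW) if there is indication of differential missingness/loss to follow-up by treatment arm (p<0.05").

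Sections 5.2 iii and iv count every child without recovery by week 12 as a failure for 24-week sustained recovery. Section 5.2 iv treats that status as certain. Children who recovered but have no 24-week measurement are excluded.

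**The concern.** Take a child seen at week 1, not recovered, who then withdraws. Week-12 status is unknown. Under 5.2 the child has a visit, so is not excluded, and has no recorded recovery, so can only be classed as not recovered. The SAP does not use the word failure, but its rule leaves no other class. That is single imputation, and it is correct only if no such child would have recovered. Under the missing-completely-at-random assumption of 4.3 these children would have recovered as often as the others, so the rule gives a biased risk difference under the plan's own assumption whenever the true difference is not zero or loss differs between arms.

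The comparison most exposed is LAF vs RUSF, which set the trial's size. Section 5.5 itself notes that bias towards the null is anti-conservative in a non-inferiority design. The trial is open-label, so different loss by arm is plausible.

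**Working it through.** **Inputs (SAP Section 3.3).** Non-inferiority: "non-inferiority margin of a risk difference of -5% is appropriate". Recovery: "60% of participants would have 12-week anthropometric recovery outcome in the RUSF and LAF arms". One-sided alpha 0.025, 90% power, 1:1 allocation, 5% loss, 2,120 per arm.

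**The plan's own figure.** n = (1.960 + 1.2816)² × 2 × 0.60 × 0.40 / 0.05² = 2,018 evaluable per arm. Dividing by 0.95 gives 2,125 and multiplying by 1.05 gives 2,119. The stated 2,120 reproduces.

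**Assumptions added here.** Lost children have the same underlying 12-week recovery probability p as others in their arm. d is the share lost after at least one visit. Loss rates other than 5% are illustrative. Normal approximation, unpooled variance, 2,120 per arm, no site effect.

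**Observed rate under the 5.2 rule, two loss timings.**
- Earliest: all loss just after visit 1, before any recorded recovery. Observed rate = p(1 - d).
- Spread: loss even over weeks 1-11, constant weekly recovery probability h = 1 - (1 - p)^(1/12), which is 0.0735 for p = 0.60 and 0.0644 for p = 0.55. Observed rate = (1 - d)p + d × m, where m is the mean of 1 - (1 - h)^k over k = 1 to 11: 0.349 for p = 0.60 and 0.314 for p = 0.55.

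**Probability of declaring non-inferiority** = P(Z > 1.96 - (RD + 0.05)/SE).

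**Equal loss of 5%, truth 60% RUSF and 55% LAF (at the margin).**
- Earliest: 0.55 × 0.95 - 0.60 × 0.95 = 0.5225 - 0.5700 = -0.0475; SE 0.0153; 1.96 - 0.0025/0.0153 = 1.80; error 3.6%.
- Spread: 0.5382 - 0.5874 = -0.0492; SE 0.0152; error 2.8%.

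**Other scenarios.**

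| Truth RUSF/LAF | Loss RUSF/LAF | Earliest: RD (points), P(declare NI) | Spread: RD (points), P(declare NI) |
|---|---|---|---|
| 60/55 | 5%/5% | -4.75, 3.6% | -4.92, 2.8% |
| 60/55 | 10%/10% | -4.50, 5.1% | -4.85, 3.1% |
| 60/55 | 5%/3% | -3.65, 14.1% | -4.45, 5.5% |
| 60/55 | 7%/3% | -2.45, 38.5% | -3.95, 10.2% |
| 60/55 | 3%/7% | -7.05, 0.05% | -5.90, 0.5% |
| 60/60 | 5%/5% | 0, 91% | 0, 91% |
| 60/60 | 3%/7% | -2.40, 40% | -1.00, 75% |

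In the 60/55 rows the last two columns show type I error (nominal 2.5%); in the 60/60 rows they show power.

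**Direction.** With equal loss and earliest timing the observed difference is (1 - d) times the true one, so it shrinks. With unequal loss it moves away from zero once LAF loss exceeds 0.60/0.55 = 1.09 times RUSF loss (earliest timing, truth at the margin).

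**The IPW trigger.** Around 5% loss, the SE of a difference in loss is √(2 × 0.05 × 0.95/2,120) = 0.0067. A gap of about 1.96 × 0.0067 = 1.3 points reaches p<0.05, and 7% vs 3% gives z = 0.04/0.0067, about 6. So the trigger would fire on a clear imbalance if these children count as lost, and would usually stay silent under equal loss.

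**The case against.** The rule is explicit and prespecified. Keeping every child with follow-up and counting unobserved recovery as non-recovery is a recognised composite-type choice that stays close to intention to treat. Children who recover before leaving are classified correctly, and counting death without recovery as non-recovery is defensible. At the SAP's 5% loss, equal in both arms, the error rises by only 0.3 to 1.1 percentage points. All of this stands. It defends the rule as a choice, but not its description as complete case without imputation, nor the lack of a sensitivity analysis that always runs.

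Three stronger readings are tempting and are not supported.

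- A reader might infer that the rule always pulls the LAF contrast towards zero. That holds only for similar loss in both arms and a non-zero true difference. With more loss on LAF the contrast can move away from zero, which is conservative for the error rate but costs power.
- A reader might take 39% error or 40% power as the expected damage. Those figures need a four-point imbalance and all loss straight after visit 1. With weekly visits and loss spread over weeks 1-11 they become about 10% and 75%.
- A reader might infer that the IPW analysis never reweights these children. Section 4.3 names loss to follow-up as well as missingness, so it may be meant to include them. The defect is that 4.3 does not say whether a child with some visits counts as missing or lost.

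**Conclusion.** The concern holds: Sections 4.3 and 5.2 contradict each other on children lost before week 12 without recovery, and 5.2 in effect imputes failure for them. It applies to both 12-week comparisons and carries into both 24-week comparisons of first-stage foods, where an unknown 12-week status is treated as a certain failure.

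The size depends on the pattern of loss. With similar loss near 5% it is slight. With loss that differs by arm it can be material in either direction. The safeguard is weak: it depends on a significance test, would usually not run under equal loss, and does not define whom it covers. Only the 5% loss figure is the SAP's. The other loss rates, the timing and equal underlying recovery in lost children are assumptions, and the 3.6% ceiling holds only under the last of these.

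**What to change.** 1. Reconcile 4.3 with 5.2: state that a child lost before recovery is scored as not recovered and that this is not a complete-case analysis. Correct the wording in 5.2 iv that treats such children's status as certain, and align 5.2 iii.
2. For both 12-week comparisons, and above all LAF vs RUSF, prespecify an analysis that runs without any p-value trigger and treats children who are alive, unrecovered and without a week-12 visit as censored or missing. Suitable forms are 12-week cumulative incidence by arm and site with death as non-recovery, or multiple imputation from the last WLZ and MUAC. Require the non-inferiority conclusion to be interpreted alongside it.
3. If IPW is kept, define missingness to include these children.

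Replacing the primary estimator is debatable and not needed to remove the contradiction. Simply excluding unrecovered lost children is not a clean repair, because early recoverers who leave stay in: at 5% spread loss the RUSF rate becomes about 60.7% instead of 60%, though the risk difference is nearly right (-4.99 points).

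The cost is SAP wording and modest programming on weekly data already collected. The added analysis relies on non-informative censoring or missing at random, which cannot be verified from the data and should be stated.

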5.3 Statistical Methods for Secondary Outcomes

We present the methods for the secondary analyses by analysis type.

i. Time-to-event analyses for first-stage and second-stage intervention effects

The following secondary outcome(s) will be analyzed with time-to-event analyses, such as time to anthropometric recovery within the first 12 weeks.

We will use Cox proportional hazard regression models that include a fixed effect for study site to account for stratified randomization to produce hazard ratios and 95% confidence intervals. The time metric for time to event analyses will be follow-up days.

Effect of first-stage and second-stage intervention effects on the change of anthropometric outcomes

We will use the analysis of covariance (ANCOVA) modelling approach, which includes the baseline score as a covariate. ANCOVA is known to have greater statistical power as compared to analysis of change from baseline [outcome is follow-up minus baseline] (Van

Breukelen 2006). Further, in an ANCOVA analysis, either the follow-up score or the change score can be used as the outcome variable, but using the change score will provide a more precise estimate if the correlation between baseline and follow-up is high (Fu and Holmer 2015). In our trial, we expect reasonably high correlation between baseline and follow-up anthropometric outcomes and will therefore use the change in anthropometric outcomes in the analysis and include baseline score as a covariate.

We will use generalized linear models with a change in anthropometric measures as the dependent variable. We will include intervention, baseline value (ANCOVA approach), and a fixed effect for study site as independent variables. We will present mean differences and 95% confidence intervals for the mean difference in change in anthropometric measures between intervention arms.

iii. Effect of first-stage and second-stage intervention effects on non-repeatable binomial We will use log-binomial regression models to present the relative risks (RR) of non-repeated secondary outcomes between groups. These outcomes include mortality, hospitalization, etc. Due to stratified randomization by study site, we will include a fixed effect for study site in the model. We will present the relative risk estimates and 95% confidence intervals.

5.4 Sensitivity Analyses for Potential Baseline Imbalance

Standard Table 1 of participant characteristics by treatment arm will not present p-values for differences between groups. In sensitivity analyses for the primary outcomes to assess the potential for baseline imbalance to affect results, we will adjust for baseline factors that showed some degree of imbalance between treatment groups based on a p<0.10. We will report the results of these sensitivity analyses and discuss if there are any qualitative differences in the findings of the baseline-adjusted and the primary analyses (unadjusted for baseline factors). If there is no evidence of baseline imbalance for the primary outcomes, we will not present baseline-adjusted analyses for secondary outcomes.

